Single Center, Randomized Prospective Comparative Effectiveness Study of Dorsal Column Spinal Cord Stimulation to Dorsal Root Ganglion Stimulation in the Treatment of Complex Regional Pain Syndrome

Version: 1.5

September 19, 2018

Department of Evidence Based Pain Research
Cleveland Clinic
[name]

Protocol Synopsis

Title:	Single Center, Randomized Prospective Comparative Effectiveness Study of Dorsal Column Spinal Cord Stimulation to Dorsal Root Ganglion Stimulation in the Treatment of Complex Regional Pain Syndrome of the Lower Extremity
Investigational Products	
 1. Nuvectra Algovita Dorsal Column Spinal Cord Stimulation System 2. Abbot Proclaim Dorsal Root Ganglion Spinal Cord Stimulation System
Regulatory Status	Post-market evaluation. The indications for both dorsal column and dorsal root ganglion neurostimulation utilized in this study are cleared by the FDA.
Study Objective:	To compare the outcomes of dorsal column stimulation with Dorsal Root Ganglion stimulation in patients with Complex Regional Pain Syndrome that persist despite a course of conservative management including physical therapy and analgesic pharmacotherapy.
Study Design:	Prospective, randomized single center study. Patients will be randomized in a 1:1 ratio to Dorsal Column or Dorsal Root Ganglion stimulation after they have failed conservative treatment.
Patient Population:	Patients with Budapest criteria (research diagnostic definition) of Complex Regional Pain Syndrome occurring below the umbilicus who have not had an adequate response to conservative management including analgesic and physical therapies.
Enrollment Size and Number of Sites:	A total of 62 patients will be recruited from a single center
Primary Outcome:	50% change in index pain using a Numerical Rating Scale (NRS) at 6 months
Secondary Outcome:	30% change in function based on Oswestry Disability Index (ODI)
Additional Assessments:	
 • Change in Quality of Life as measured by EQ-5D • Change in Health Status measured by Short Form-36 (SF-36) • Pre and Post Procedure Pain medication usage • Global Improvement Impression of Change (PGIC) • Satisfaction with the pain relief, therapy in general, and likelihood of undergoing the therapy again for a similar outcome • Neurological assessment • Additional intervention(s)

	
 • Safety defined as adverse events related to the procedure or devices
Inclusion Criteria	
All patients must meet all of the following Inclusion Criteria to be eligible to be enrolled into the study:
 
 • Patient is greater than 18 years of age • An infraumbilical location of the index pain • Symptoms have been present for greater than 6 months • Continuing pain which is disproportionate to any inciting event • Report hyperesthesia and/or allodynia • Report vasomotor changes including temperature asymmetry and/or skin color changes and/or skin color asymmetry • Report edema and/or sweating changes and/or sweating asymmetry • Report decreased range of motion and/or motor dysfunction (weakness, tremor, dystonia) and/or trophic changes (hair, nail, skin) • Display at least one sign in two or more of the following categories: 
 ○ Sensory: Evidence of hyperalgesia (to pinprick) and/or allodynia (to light touch and/or temperature sensation and/or deep somatic pressure and/or joint movement) ○ Vasomotor: Evidence of temperature asymmetry (>1°C) and/or skin color changes and/or asymmetry ○ Sudomotor/Edema: Evidence of edema and/or sweating changes and/or sweating asymmetry ○ Motor/Trophic: Evidence of decreased range of motion and/or motor dysfunction (weakness, tremor, dystonia) and/or trophic changes (hair, nail, skin) • Patient failed to have resolution of symptoms despite at least 4 weeks of conservative management including analgesic pharmacotherapy and physical therapy • Patient has index site pain \geq spine pain • The subject is physically and mentally able to participate in the study • Patient is willing and able to provide informed consent • Patient is willing and able to comply with the study protocol
Exclusion Criteria	
All patients who meet any of the following Exclusion Criteria should not be enrolled into the study:
 
 • Previous surgery to the spine which could compromise placement of the study device

	
 • Anatomical spinal abnormality including severe central canal stenosis or bony foraminal impingement which could preclude device placement • Foreseen need for MRI to monitor or evaluate another chronic condition • Previous experience with an implanted or trial neuromodulation system (spinal cord stimulation, peripheral nerve stimulation) for the treatment of pain at the index location • Active local or systemic infection • Actively in litigation for pain symptoms • Currently on Workman’s Compensation • Women who are pregnant or intend to become pregnant during the study duration
Study Duration / Follow-up Period	Patients will be followed for an additional 6 months after device implant, with visits at 10 and 30 days, and 3 and 6 months post-procedure. Interim visits for device programming visits will be considered routine.
Baseline Visit	
 • Demographics: gender, age, height, weight • History • Characterization of the inciting event including duration of pain symptoms • Previous treatments including conservative management and physical therapy • Diagnosis and review of the inclusion and exclusion criteria • Neurological assessment • NRS for the index pain location • Pain medication usage (dosage and frequency)
Psychological Assessment	Psychological assessment will consider appropriateness for a neuromodulation system and for participation in a clinical device study.
Pre Trial Visit	
 • Neurological assessment • NRS for the index pain location • ODI • EQ-5D • SF-36 • Satisfaction with baseline management strategy • Pain medication usage (dosage and frequency)

	
 • Presurgical trial evaluation as stratified by the investigator including advanced imaging if necessary • Randomization
Trial Procedure	
 • Neurological assessment • NRS for the index pain location • Pain medication usage (dosage and frequency) • Trial of the study device
Trial Device Removal (7 days postop +/- 3 days)	
 • Wound check, trial device removal • NRS for index site pain • Neurological assessment • Additional intervention(s) • Complications / Adverse events
Pre Implant Visit	
 • Neurological assessment • NRS for the index pain location • ODI • EQ-5D • SF-36 • Satisfaction with present management strategy • Pain medication usage (dosage and frequency) • Presurgical medical evaluation, history and physical examination, and additional special tests as stratified by the investigator including laboratory analysis, EKG, infectious screening, and/or advanced imaging
Implant Procedure	
 • Neurological assessment • NRS for the index pain location • Pain medication usage (dosage and frequency) • Implantation of the study device
Post-Operative Follow-up Visit (10 days postop +/- 3 days)	
 • Wound check, suture removal • NRS for index site pain • Neurological assessment • Additional intervention(s) • Complications / Adverse events
Follow-up Visit (30 days +/- 7 days)	
 • NRS for index site pain • Neurological assessment • ODI • EQ-5D

	
 • SF-36 • Pain medication usage (dosage and frequency) • PGIC • Additional intervention(s) • Complications / Adverse events • Radiograph to evaluate lead(s) position
Follow-up Visit (3 month +/- 14 days)	
 • NRS for index site pain • Neurological assessment • ODI • EQ-5D • SF-36 • Pain medication usage (dosage and frequency) • PGIC • Satisfaction questionnaire • Additional intervention(s) • Complications / Adverse events
Follow-up Visit (6 month +/- 14 days)	
 • NRS for index site pain • Neurological assessment • ODI • EQ-5D • SF-36 • Pain medication usage (dosage and frequency) • PGIC • Satisfaction questionnaire • Additional intervention(s) • Complications / Adverse events
Anticipated Unscheduled Visits	
 1. Radiograph to evaluate device positioning 2. Ad hoc programming of the study device
Site	Department of Evidence Based Pain Research Cleveland Clinic [name]

Table of Contents

1	INTRODUCTION	9
1.1	Background and Rationale.....	9
2	DEVICE DESCRIPTION.....	9
2.1	Device Indications for Use.....	9
3	STUDY PURPOSE AND OBJECTIVE.....	10
4	STUDY ENDPOINTS	10
4.1	Primary Endpoint.....	10
4.2	Additional Assessments.....	10
5	STUDY DESIGN.....	10
5.1	Overview.....	10
5.2	Sample Size and Number of Centers.....	11
5.3	Study Duration.....	11
6	STUDY PROCEDURES	12

1 INTRODUCTION

1.1 Background and Rationale

Complex Regional Pain Syndrome (CRPS) is a constellation of pain symptoms which are associated with impairment in mood, social and physical function (Harden, et al. 2007) (Deer, Levy and Kramer 2017) (Banks and Kerns 1996) (Modovan, et al. 2009). Spinal Cord Stimulation (SCS), a technique of placing electrodes into the epidural space is a validated treatment for Complex Regional Pain Syndrome (Deer, et al. 2014). Treatment of CRPS with SCS, in combination with physical therapy, reduced pain to a greater degree than physical therapy alone (Kemler, et al. 2000). 40%-50% of CRPS patients achieve >50% pain relief with SCS using dorsal column stimulation (Kemler, et al. 2000) (Geurts, et al. 2013). Dorsal Root Ganglion (DRG) SCS has also recently demonstrated clinical efficacy in patients with CRPS and peripheral causalgia (Deer, Levy and Kramer 2017) (Van Buyten, et al. 2015). We hypothesize that DRG stimulation is non-inferior to dorsal column SCS in patients with CRPS who have failed to respond to a course of analgesics and physical therapy. Additionally, we aim to assess functional, quality of life, patient satisfaction and medication requirements in subjects treated with neuromodulation for CRPS and contrast outcomes amongst subjects treated with DRG SCS and dorsal column SCS.

2 Device Indications for Use

DEVICE DESCRIPTIONS

See the manufacturer's Instructions for Use and Surgical Technique Manual for more detailed information.

The Nuvectra Algovita Dorsal Column Spinal Cord Stimulator is indicated as an aid in the management of chronic intractable pain of the trunk and/or limbs, including unilateral or bilateral pain associated with failed back surgery syndrome, intractable low back pain and leg pain.

The Axiom Neurostimulator System is indicated for spinal column stimulation via epidural and intra-spinal lead access to the dorsal root ganglion as an aid in the management of moderate to severe chronic intractable pain of the lower limbs in adult patients with Complex Regional Pain Syndrome Types I and II

Systems that will be utilized in this study are indicated for use in this condition and have already been cleared for marketing by the FDA.

3 STUDY PURPOSE AND OBJECTIVE

The purpose of this study is to compare outcomes between dorsal column spinal cord stimulation and dorsal root ganglion spinal cord stimulation in patients with Complex Regional Pain Syndrome at an infraumbilical location who have failed a course of conservative management including analgesic pharmacotherapy and physical therapy.

4 STUDY ENDPOINTS

The following endpoints will be evaluated in all patients enrolled in the study.

4.1 Primary Endpoint

- The primary endpoint in this study is 50% change in index pain using a Numerical Rating Scale (NRS) at 6 months

4.2 Additional Assessments

[figure not shown]
- Change in function based on Oswestry Disability Index (ODI)
- Global Improvement Impression of Change (PGIC)
- Change in Quality of Life as measured by EQ-5D
- Pre and Post Procedure Pain medication usage (dosage and frequency)
- Patient Satisfaction
- Procedure time
- Neurological assessment
- Additional intervention(s)
- Safety defined as adverse events related to the procedure or device

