6.3 Randomization

After informed consent has been obtained, patients will be randomized in a 1:1 ratio to one of two treatment groups: Dorsal Column Stimulation or Dorsal Root Ganglion Spinal Cord Stimulation. The investigator will be given numbered, sealed envelopes with a slip inside that discloses the patient assignment.

If a patient randomized to either group refuses the proposed treatment plan, they will be removed as a study participant. Patients withdrawing from the study due to randomization assignment will receive standard care with a new randomization code being assigned to the next enrolled study patient.

Investigators, their study staff, as well as study subjects will not be masked to the assigned study device. Observers will record sensory deficits to touch, pain, temperature, motor strength of major muscle groups, patient reflexes (0-4 scale), analgesics doses and frequency, and radiographic assessments if necessary. Subjects will complete the patient questionnaires at each follow-up visit.

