10 ADVERSE EVENTS

10.1 Definitions

10.1.1 Adverse Events

Adverse events (AE) are any untoward medical occurrence, unintended disease or injury, or untoward clinical signs (including abnormal laboratory findings) in which subjects, users or other persons, whether or not related to the investigational medical device.

All adverse events, regardless of relationship to the device, must be recorded, as applicable, on the case report forms provided. Adverse events that occur during this study should be treated by established standards of care, which will protect the life and safety of the patients.

Adverse events shall be assessed and documented at the time of the procedure and at all study follow-up visits.

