10.2 Adverse Event Reporting

Any adverse event that occurs during the course of the study must be reported using the appropriate forms. The Investigator must determine whether the adverse event is serious or unanticipated, its intensity, and the relationship of each adverse event to the study device and/or procedure.

For any adverse event that is ongoing at the time of the initial report, periodic follow-up information is required until the adverse event is resolved or is judged to be chronically stable.

The Investigator will report all serious adverse events, including unanticipated adverse device effects, to the IRB according to the IRB requirements.

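### The specified safety outcome counts only adverse events that an unmasked investigator judges related, although all events are recorded, so it is open to differential attribution between the arms

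*Combined protocol and SAP*

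**What the plan says.** Section 4.2 lists the safety item as "Safety defined as adverse events related to the procedure or device", and the synopsis has the same restriction: "Safety defined as adverse events related to the procedure or devices".

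Collection is wider than the outcome. Section 10.1.1 states: "All adverse events, regardless of relationship to the device, must be recorded, as applicable, on the case report forms provided". The same section has events assessed at the procedure and at every follow-up visit.

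Section 10.2 assigns the classification to the investigator, who rules on seriousness, expectedness, intensity and "the relationship of each adverse event to the study device and/or procedure". Section 6.3 removes masking: "Investigators, their study staff, as well as study subjects will not be masked to the assigned study device".

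The document gives no causality categories or criteria, no events committee and no masked or independent review of relatedness. Section 8.4 supplies general methods for categorical outcomes (chi-square or Fisher exact) and does not mention safety.

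**The concern.** The trial compares two implanted stimulators, and section 3 makes comparison of outcomes its purpose. Randomization supports a comparison of what happens to patients in each arm. It does not support a comparison of what someone who knows the arm later attributes to the device. A relatedness filter puts that judgement between the event and the outcome, and the plan neither standardizes the judgement nor masks it.

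The filter matters most where device effects and disease look alike. To be eligible, a patient must report symptoms in all four categories: sensory, vasomotor, edema or sweating, and motor or trophic, the last of which can include weakness. Section 7.2 lists nerve root irritation or injury, with or without deficit, among the risks. New weakness or altered sensation after a lead is placed could be called a device effect or CRPS. If that call is made differently in the two arms, the related-event counts can differ when the event counts do not, or agree when the event counts differ.

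**Working it through.** The plan states no safety figure, so there is nothing to reproduce. The check compares the sections and then illustrates how large the effect could be.

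**Comparison of the sections**

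1. Outcome: related events only (synopsis, 4.2).
2. Data: all events (10.1.1), so the outcome is a subset of what is collected.
3. Who selects the subset: the investigator, event by event (10.2).
4. What the investigator knows: the assigned device (6.3).
5. Safeguard on the selection: none described in 6.3, 8.4 or 10.
6. Other route to an all-event comparison: none specified. Section 10.2 says "The Investigator will report all serious adverse events, including unanticipated adverse device effects, to the IRB according to the IRB requirements", but that is a reporting duty and does not define an outcome by arm.
7. Unfiltered items: 4.2 separately lists the neurological assessment and additional interventions. Table 1 has the neurological assessment at every visit. Sections 6.3 and 6.4 include sensory testing, motor strength (graded 0 to 5, with a pre-operative value) and reflexes. None of these needs a causality call.

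**Illustration**

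Input from the plan: 31 per arm (5.2). Assumed, and not in the document: the all-cause event proportion p, equal in both arms, and the shares s1 and s2 of patients with an event whose event is called related in each arm.

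Related proportion in arm i = p × si. Apparent risk ratio = s1/s2. Half-width of the 95% interval for the difference, with qi = p × si, is 1.96 × √{[q1(1−q1) + q2(1−q2)]/31}.

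| p | s1, s2 | Related, arm 1 v arm 2 | Difference (points) | Risk ratio | Half-width (points) |
|---|---|---|---|---|---|
| 30% | 90%, 70% | 27% v 21% | 6 | 1.29 | 21 |
| 30% | 90%, 50% | 27% v 15% | 12 | 1.80 | 20 |
| 50% | 90%, 70% | 45% v 35% | 10 | 1.29 | 24 |
| 50% | 90%, 50% | 45% v 25% | 20 | 1.80 | 23 |

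The true all-cause difference is zero in every row.

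In counts, suppose 8 of 31 patients in each arm have an event, and all 8 are called related in one arm but 4 in the other. The outcome reads 8/31 = 25.8% against 4/31 = 12.9%. The difference is 12.9 points, with 95% interval 12.9 ± 19.4, or −6.5 to 32.3, and Fisher p = 0.34.

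Uneven labelling can thus move the point estimate noticeably, yet at this sample size none of these gaps could be told from chance.

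**The case against.** **Related events are a recognizable way to define device safety.** This stands, and the related-event table should be kept. The difficulty is that it is the only safety outcome defined, in an open-label comparison.

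**Most listed hazards are hard to mislabel.** This also stands. Infection, dural tear or CSF leak, seroma or hematoma, vascular injury and bleeding (7.2) are procedural, and CRPS does not mimic them. A reader might infer that the main hazards are generally hard to attribute. The document supports that mainly for neurological symptoms.

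**Neurological change is captured elsewhere.** Largely true. The neurological assessment and additional interventions carry no relatedness filter and can be compared by arm, although they too are observed unmasked. This reduces the problem without removing it, because they are not the stated safety outcome.

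**No filtered between-arm report is actually promised.** True. The plan writes out no safety table or test. That a between-arm comparison is intended is inferred from section 3 and the general methods in 8.4. A reader might conclude that all-event results will not be reported, but nothing prevents an all-event table. The plan simply does not specify one.

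**There is no evidence of differential labelling.** Correct. Both arms receive active implanted devices at one center, and the document gives no reason to expect bias in either direction. A reader might infer that attribution alone will produce or hide a safety difference. The attribution shares above are assumptions, and the resulting gaps lie within random error.

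**An all-event count is not fully protected either.** Events are still reported and recorded open-label. Section 6.5 allows crossover after a failed trial, and 6.3 removes patients who refuse their assignment. The change removes the attribution step and leaves these limits in place.

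**Conclusion.** The point holds as a risk of bias in the definition of one additional assessment. The specified safety outcome depends on relatedness calls made by an investigator who knows the arm, with no stated criteria and no independent review, while the unfiltered data are already collected.

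The size and direction of any bias are unknown. The risk ratios of 1.29 and 1.80 show only what the assumed attribution shares would do. Exposure is concentrated in events that overlap with CRPS, and the separate neurological and additional-intervention assessments reduce it further. A reader might take the point to undermine the trial's main result. It does not, because the primary endpoint is NRS response and the noninferiority conclusion is untouched.

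The conclusion assumes that safety will be compared between arms, which the plan implies but does not write out. The change is worth making because it is cheap, and it is more credible if fixed before results are seen.

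**What to change.** In the synopsis and section 4.2, define safety as all adverse events and all serious adverse events from the first trial procedure to the end of follow-up, reported by randomized arm regardless of relatedness. Keep investigator-judged related events as a secondary breakdown. Show events after crossover also by the device in place at onset. State when the reporting window closes for patients who are never implanted, because section 5.3 times the follow-up visits from implant.

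The cost is a wording change and added tables from data that 10.1.1 already requires, with no new visits. The downside is that background CRPS events add noise to the all-event counts, which is why the related-event breakdown stays alongside. Event reporting itself remains open-label, and the text should say so.

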5 STUDY DESIGN

5.1 Overview

This is a prospective randomized post-marketing clinical study. Patients will be randomized in a 1:1 ratio to Dorsal Column or Dorsal Root Ganglion Spinal Cord Stimulation if they have failed a course of conservative management including analgesics and physical therapy. All patients are expected to undergo clinical, neurological, and imaging assessments, if appropriate, at selected follow-up visits.

Figure 1. Study Design Flow Chart

5.2 Sample Size and Number of Centers

The study will be conducted a single center with a target maximum of 62 patients (31 randomized to each group).

5.3 Study Duration

Enrollment of subjects in this study is anticipated to take 24 months. Clinical follow-up evaluations will be conducted at 10 days, 1, 3 and 6 months post-implant. The total study duration is expected to be at least 30 months.

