6.5 Procedure

The appropriate procedure will be performed based on the randomization assignment for each patient. Patients randomized to either group will have the device trialed, then implanted according to the standard procedures and practices at our institution.

Those who fail to respond to a trial of the randomized device will have the opportunity to cross over, and retriage the alternative device. Should they have favorable response to the second device, they will proceed to implant of the alternative system.

Any female patient of child bearing age who does not have a documented history of surgical sterilization will have a urine pregnancy test performed within two hours before the device is trialed or implanted.

Pain medications may be administered at the investigator's or prescriber's discretion. A pain medication log will be given to the patient. Continuous pain medication usage will be documented. The treating physician may continue to pharmaceutically manage the patient's pain through the length of the study as clinically indicated. Use of pain medications after either intervention, when compared to pre-intervention dosing, will be considered. The investigator or research coordinator will review the study requirements with the patient in order to maximize compliance with the follow-up schedule and the concomitant medical regimen.

The following parameters for both groups will be noted on the case report forms:

- Index pain location
- Procedure time
- Physical/Neurological Exam
- Complications / Adverse events
- Radiographic Assessment confirming appropriate device placement
- Pain medications

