6.6 Post Procedures and Outcomes

Follow-up visits are scheduled for appointed times after the date of the procedure. It is important that this schedule is adhered to as closely as possible for all subjects. Study visits not completed within these time periods will be regarded as deviations. A study visit should be scheduled as closely as possible to the earlier part of the time period to allow for possible re-scheduling, thereby preventing a deviation. All subjects will be asked to return to the clinic at intervals described in **Table 1**. Device programming and radiographic lead positioning confirmation visits are anticipated unscheduled visits and do not represent protocol deviations, and may occur *ad hoc*.

The following post-operative data will be collected:

- NRS for the index site pain
- ODI
- EQ-5D
- Global Improvement Impression of Change (PGIC)
- SF-36
- Pain medication usage (dosage and frequency)
- Neurological assessment
- Patient Satisfaction
- Additional intervention(s)
- Complications / Adverse events

Table 1: Schedule of Assessments

Assessment									
	Pre-op	Trial Procedure	Trial Removal Follow-up 7 (+/- 3 days)	Implant Procedure	Post-Operative Follow-up 10 (+/- 3 days)	Follow-up Visit (30 days +/- 7 days)	Follow-up Visit (3 months +/- 14 days)	Follow-up Visit (6 months +/- 14 days)	Unscheduled Visit
Informed Consent	X								
Medical & Interval History	X	X	X	X	X	X	X	X	X
Demographics	X								
Physical Exam / Neurological Assessment	X	X	X	X	X	X	X	X	X
Pain Scales (NRS) & Pain Medication Usage	X	X	X	X	X	X	X	X	X
Oswestry Disability Index (ODI)	X					X	X	X	
EQ-5D	X					X	X	X	
Global Improvement Impression of Change (PGIC)			X		X	X	X	X	
SF-36						X	X	X	
Patient Satisfaction	X		X		X	X	X	X	
Adverse Events*	X	X	X	X	X	X	X	X	X
Other Interventions		X	X	X	X	X	X	X	X

*Adverse events should be recorded at any time during the course of the study

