7.2 Risks

Possible risks associated with neuromodulation in either arm include:

- Failure to relieve pain
- Unable to place the device due to anatomical abnormality
- Infection
- Dural tear / CSF leak
- Nerve root irritation or nerve root injury with or without neurological deficit
- Seroma / Hematoma
- Vascular injury
- Bowel / bladder incontinence
- Bleeding
- Epidural fibrosis

Mean radiation exposure with spinal cord stimulation has been estimated at 13.9mGy, range: 1.8mGy-43.7mGy (Wininger, Deshpande and Deshpande 2010).

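### A patient who has trial leads placed but is never implanted has no scheduled adverse event assessment after lead removal at day 4 to 10

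*Combined protocol and SAP*

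**What the plan says.** Section 5.3 sets the follow-up clock: "Clinical follow-up evaluations will be conducted at 10 days, 1, 3 and 6 months post-implant". The synopsis does the same: "Patients will be followed for an additional 6 months after device implant". Section 6.6 is less specific ("Follow-up visits are scheduled for appointed times after the date of the procedure") and does not say which procedure is meant. Table 1, in the same section, places the 10-day, 30-day, 3-month and 6-month columns after the Implant Procedure column.

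The one visit that follows the trial procedure for everyone is listed in the synopsis as "Trial Device Removal (7 days postop +/- 3 days" (in days, counted from the trial). Its content includes "Wound check, trial device removal", a neurological assessment and adverse events.

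Section 6.5 foresees trial failure: "Those who fail to respond to a trial of the randomized device will have the opportunity to cross over". A patient who responds to the second device goes on to implant. Nothing is said about a patient who declines the crossover or fails both trials.

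On safety, section 10.1.1 states: "Adverse events shall be assessed and documented at the time of the procedure and at all study follow-up visits". Section 4 says its endpoints are evaluated in all enrolled patients, and section 4.2 lists procedure- or device-related adverse events among them. Section 7.2, under "Possible risks associated with neuromodulation in either arm include", names infection, CSF leak, hematoma and nerve root injury. It also names failure to relieve pain and inability to place the device.

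**The concern.** Placing trial leads is itself an invasive procedure, and the listed risks are not confined to the implant. Some of those events could first appear after the leads are out. An implanted patient is seen four more times over 6 months. A patient whose trial fails and who is not implanted is seen at removal and then has no scheduled contact.

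Safety is a named between-arm assessment. If active questioning stops early for patients who are not implanted, the count of procedure-related events depends partly on how long each patient was asked. Should trial failure be more common with one device, ascertainment would differ between the randomized arms as well. Events not asked about at the time cannot be reliably recovered at analysis.

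**Working it through.** **Step 1: the removal window.** The plan's figure is 7 +/- 3 days after the trial procedure: 7 - 3 = 4 and 7 + 3 = 10. The last visit that a never-implanted patient is sure to have therefore falls on day 4 to day 10 after lead placement, on the day the leads come out.

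**Step 2: count scheduled visits after removal.**

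| Patient | Scheduled follow-up visits after removal |
|---|---|
| Responds and is implanted | 10 days, 30 days, 3 months, 6 months: 4, plus pre-implant and implant contacts |
| Fails, crosses over, responds, is implanted | The same 4, counted from the implant |
| Fails and declines crossover, or fails both trials | 0 |

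The synopsis also lists a Pre Implant Visit, but that applies only to patients going on to implant.

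**Step 3: does other safety text supply a contact?**

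- The Table 1 footnote allows adverse events to be recorded whenever they occur. It permits recording but schedules no enquiry.
- The Unscheduled Visit column includes examination and adverse events. The unscheduled visits that section 6.6 anticipates are for device programming and for checking lead position, neither of which arises once the leads are out.
- Section 10.2 requires any adverse event during the study to be reported, and requires follow-up of an event still open at its first report. An event that begins after removal has no first report unless the patient comes forward.
- The telephone attempts in section 6.8 respond to missed visits. A patient with no scheduled visit cannot miss one.

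None of these creates a scheduled assessment after removal.

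**Step 4: how many patients.** The documents give no trial-failure rate and no crossover uptake or success rate, so both proportions below are assumptions. Affected patients = 62 x (proportion failing the first trial) x (proportion of those never implanted).

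| First-trial failure (assumed) | Failing first trial, of 62 | 25% never implanted | 50% never implanted | 100% never implanted |
|---|---|---|---|---|
| 10% | 6.2 | 1.55 | 3.1 | 6.2 |
| 20% | 12.4 | 3.1 | 6.2 | 12.4 |
| 30% | 18.6 | 4.65 | 9.3 | 18.6 |

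The range is about 2 to 19 of 62. The upper end requires that 30% fail the first trial and that none of them is later implanted. Patients whose device could not be placed are not in this count.

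**Step 5: direction.** An arm with more first-trial failures would contain more patients with short observation and no implant procedure, which lowers its event count. It would also contain more crossovers, who have a second lead procedure and possibly an implant. Those events count toward the randomized arm and raise its total. The net sign depends on crossover uptake and second-trial success, and the documents give neither.

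**The case against.** The strongest reply is that the protocol already intends safety follow-up for everyone. Section 4 covers all enrolled patients, sections 10.1.1 and 10.2 require every adverse event to be recorded and reported, and the removal visit has a real safety check. Both devices are marketed. Section 6.6 does not say which procedure starts the clock, so the visits might be meant to run for everyone.

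Part of this stands. Safety capture is not absent: an event the patient reports while still in the study can be recorded, and a known open event must be followed. What is missing is active, scheduled questioning. The open wording in 6.6 does not rescue the plan, because section 5.3, the synopsis and the column order of Table 1 all point to implant.

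A reader might go further in four ways that the documents do not support:

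- That a crossover's second trial goes unassessed. Table 1 has one Trial Procedure and one Trial Removal column, but a schedule normally lists each visit type once, and section 6.5 has the patient repeat the trial. Section 10.1.1 on its face covers a second procedure. The flow chart (Figure 1) is not available in the text reviewed and may show this path. This needs clarification only.
- That the adverse event comparison rests almost wholly on implanted patients. Table 1 marks adverse events at the trial procedure and at removal for everyone trialled.
- That the arm with more failed trials will look safer. Step 5 of the working shows that the sign is undetermined.
- That every first-trial failure (about 6 to 19) loses follow-up. Only those never implanted do.

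**Conclusion.** The point holds as a gap in scheduled safety ascertainment. Followed exactly, the plan gives a never-implanted patient no scheduled adverse event assessment after the removal visit at day 4 to 10, while an implanted patient has four further visits over 6 months. That does not fit with evaluating safety in all enrolled patients.

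Ascertainment differs by implant status with certainty, and by randomized arm only if trial failure differs by arm. No direction of bias can be stated. The size, about 2 to 19 of 62 patients, rests on two assumed proportions (10% to 30% failing a first trial, and 25% to 100% of those never implanted) and should be read as a range of possibilities, not a forecast.

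This is a cheap improvement to data collection and does not call the design into question. It concerns safety only. The same missing time anchor also leaves the 6-month pain assessment undefined for these patients, so settling the anchor may help there too.

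**What to change.** - Add to Table 1 and section 6.6 a scheduled adverse event contact, by telephone, for every patient who had a trial but was not implanted. The sponsor should set its timing so that it is comparable with an existing post-implant check.
- Report adverse events for all patients who had a lead placed, and state the observation time in each arm, so that unequal follow-up is visible.
- As a clarification, state that the Trial Procedure and Trial Removal assessments repeat at a crossover's second trial.
- Reconcile sections 5.3, 6.5, 6.6 and Table 1 on the starting point for follow-up and on what is scheduled after a declined crossover or a second failed trial.

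The cost is one call each for an assumed 2 to 19 patients, a schedule entry and one more column in the adverse event report. Treatment, primary endpoint and sample size are unchanged. The downside is a little coordinator time.
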